9.4 Treatment(s)

9.4.1 Treatment(s) Administered

Core Study

For this study, the test drug is elenbecestat and the control drug is placebo. All study drug is to be administered orally, once daily (QD), in the morning with or without food. As shown in [Figure 1](#), there will be 2 treatment arms where the elenbecestat arm will be administered a single dose of 50 mg per day and the control arm will be administered placebo.

Study treatment will begin on Day 1 (at the study site) following randomization and will continue for approximately 24 months. Please refer to [Table 5](#) and [Section 9.5.1.4.1](#) for specific information regarding study drug administration on days when PK sampling is to be performed.

Study drug dose will remain the same for each individual subject throughout the duration of the study. If a subject develops a concurrent illness during the Treatment Period, the investigator should discuss with the medical monitor whether dosing with study drug needs to be temporarily suspended. As a general clinical guideline, dosing with study drug may be resumed after resolution or stabilization of the concurrent illness, after discussion with the medical monitor.

Rules for discontinuing study treatment for subjects due to skin rash or to severe infections are described in [Section 9.5.1.5.5](#).

For details on treatment to be administered in the Extension Phase, refer to [Appendix 5 in Section 12](#).

9.4.2 Identity of Investigational Product(s)

Core Study

Elenbecestat will be supplied by the sponsor as tablets of 50-mg dose strength in bottles of 35 tablets each. Placebo tablets to match elenbecestat will be of identical appearance. Each subject will receive 1 tablet of 50 mg elenbecestat or an identical placebo tablet, to be administered orally QD in the morning with or without food. The product release certificates for elenbecestat and placebo will be included in the clinical study report for this protocol.

Subjects will be stratified and randomized, and drug will be dispensed, via an interactive voice and web response system (IxRS) system (see [Section 9.4.3](#)).

The sponsor will provide the study drugs packaged in a double-blind configuration. Each subject's study tablets will consist of either elenbecestat or placebo (see [Section 9.4.2.3](#) for labeling details).

9.4.2.1 Chemical Name, Structural Formula of Elenbecestat

- Test drug code: E2609
- Generic name: elenbecestat
- Chemical name: International Union of Pure and Applied Chemistry
N-{3-[(4*aS*,5*R*,7*aS*)-2-Amino-5-methyl-4*a*,5-dihydro-4*H*-furo[3,4-*d*][1,3]thiazin-7*a*(7*H*)-yl]-4-fluorophenyl}-5-(difluoromethyl)pyrazine-2-carboxamide
- Molecular formula: C₁₉H₁₈F₃N₅O₂S
- Relative molecular mass: 437.44

9.4.2.2 Comparator Drug

Not applicable.

9.4.2.3 Labeling for Study Drug

Elenbecestat will be labeled in accordance with text that is in full regulatory compliance with each participating country and is translated into the required language(s) for each of those countries. The following information may be included but is not limited to:

- Protocol number
- For clinical study use only
- Name and address of the sponsor
- Chemical name/drug identifier
- Lot number/batch number
- Storage conditions, expiration date if necessary

9.4.2.4 Storage Conditions

Study drug will be stored in accordance with the labeled storage conditions. Temperature monitoring is required at the storage location to ensure that the study drug is maintained within an established temperature range. The investigator or designee (or if regionally required, the head of the medical institution) is responsible for ensuring that the temperature is monitored throughout the total duration of the study and that records are maintained; the temperature should be monitored continuously by using either an in-house validated data acquisition system, a mechanical recording device, such as a calibrated chart recorder, or by manual means, such that minimum and maximum thermometric values over a specific time period can be recorded and retrieved as required.

9.4.3 Method of Assigning Subjects to Treatment Groups

Subjects will be assigned to treatments based on a computer-generated randomization scheme that will be reviewed and approved by an independent statistician. The randomization scheme and identification for each subject will be included in the final clinical study report for this study. The doses and number of treatment groups to be used are described in [Section 9.4.1](#).

Stratification and randomization will be performed centrally by an IxRS. The IxRS or clinical supply vendor will generate the randomized bottle identification numbers. At enrollment (Screening), the investigator or designee will call the IxRS to register the subject information. At randomization (Visit 2), the IxRS will assign each subject a unique randomization number.

9.4.4 Selection of Doses in the Study

Selection of elenbecestat 50 mg per day is based on the results (PD, safety, and tolerability) from the completed Phase 1 studies and interim data from the ongoing Phase 2 Study 202. Study 202 has been completed, and a study report is in preparation. It evaluated the PD effects (reduction from baseline in CSF A β levels) along with safety and exploratory efficacy of 5, 15, and 50 mg of elenbecestat given daily. Based on the PK/PD modeling results,

elenbecestat 50 mg per day reduced median CSF A β by approximately 70%. (revised per Amendment 03) Based on these data, elenbecestat 50 mg per day dose was selected as a viable dose for this study. Subjects will be stratified according to region (7 levels), clinical dementia staging with no more than approximately 25% of the randomized subjects diagnosed with the early stages of mild dementia due to AD, and concurrent AD medication use. (revised per Amendments 01 and 02)

9.4.5 Selection and Timing of Dose for Each Subject

Elenbecestat is administered orally, QD, in the morning with or without food. Study treatment will begin on Day 1 following randomization and will continue for 24 months.

9.4.6 Blinding

Elenbecestat and placebo will be administered as tablets of identical appearance.

During the Randomization and Follow-up Phases, subjects and all personnel involved with the conduct and interpretation of the study, including investigators, site personnel, and sponsor staff will be blinded to the treatment codes (double-blind). Randomization data will be kept strictly confidential, filed securely by an appropriate group with the sponsor or CRO, and accessible only to authorized persons (eg, Eisai Global Safety) until the time of unblinding, per the standard operating procedure.

PK and PD data will be provided to the sponsor by the PK and PD analysis laboratories using dummy subject numbers instead of actual subject numbers. The same dummy subject number will be used for a subject's PK and PD data. These data will be used to evaluate whether the PK and PD effects seen in this study are similar to those seen in previous studies. Thereafter, unblinded PK and PD data will only be provided to the sponsor after study completion.

In the event that emergency conditions require knowledge of the study treatment given, the blind may be broken via the code breaker facility within the IxRS. Emergency procedures for revealing drug codes are given in [Section 9.5.4.5](#). If possible, before breaking the blind, the investigator should consult with the sponsor to ascertain the necessity of breaking the code. If an AE results in the investigator breaking the blind, then that AE must be reported as a SAE.

9.4.7 Prior and Concomitant Therapy

Any medication (including over-the-counter medications) or therapy administered to the subject before the study (within 6 months of randomization) and during the study (starting at the date of informed consent) will be recorded on the Prior & Concomitant Medication eCRF or Non-Pharmacological Procedures eCRF. The investigator will record on the Adverse Event eCRF any AE for which the concomitant medication/therapy was administered. If the concomitant medication/therapy is being administered for a medical condition present at the time of entry into the study, the investigator will record the medical condition on the Medical History and Current Medical Condition eCRF.

Listings of prohibited and permitted drugs are provided in [Appendix 2](#) (Prohibited medications are presented in [Listing 1](#), [Listing 2](#), and [Listing 3](#). Medications that are permitted with restrictions are listed in [Listing 4](#), [Listing 5](#), and [Listing 6](#)).

The following agents are not permitted before randomization (specific time frames are shown below) and until the last visit during the Treatment Period: (revised per Amendment 02)

- a) Immunoglobulin therapy and biologic drugs are not permitted within 6 months before Screening and until the last visit during the Treatment Period (revised per Amendment 02)
- b) Systemic immunosuppressive or immunomodulatory drugs are not permitted for a period of 5 half-lives or 60 days (whichever is longer) before randomization and until the last visit during the Treatment Period (revised per Amendments 02 and 04)
- c) Moderate to strong inhibitors of carboxylesterase 2 (CES2) enzyme activity are not permitted for a period of 5 half-lives or 7 days (whichever is longer) before randomization and until the last treatment visit. Simvastatin use is permitted only with QD evening administration.
- d) Live/live attenuated vaccines are not permitted within 3 months before randomization and until the last treatment visit (this does not apply to non-live/inactivated vaccines) (revised per Amendment 02)

Concomitant therapy with AChEI or memantine should only be allowed and/or acceptable for the region or country in which the study is being conducted and should follow the local standard of care for symptomatic treatment (revised per Amendment 02). Subjects who are taking AChEI or memantine will be required to be on a stable dose for at least 12 weeks before randomization. Initiation or termination of therapy or changing dose of AChEIs or memantine during the study should be undertaken in compliance with local standard of care for symptomatic treatment of AD. (revised per Amendments 03 and 06) Subjects who start on AChEI or memantine or change their dose during the Treatment Period will be permitted to continue in the study; however, subjects should not undertake cognitive assessments until they have been on a stable dose for at least 4 weeks.

Subjects who are taking other medications will be required to be on a stable dose for at least 4 weeks before randomization, except for medications which are administered as short courses (eg, up to 3 weeks unless discussed and agreed with the medical monitor) of treatment (eg, anti-infectives, oral steroids) or which are to be used on a PRN basis. (revised per Amendment 01) Concomitant medications (including opiates and short-term use of benzodiazepines) which are used on a PRN basis and which are central nervous system (CNS) active and may affect cognitive function are not permitted during a period of 72 hours before cognitive testing. (revised per Amendments 04 and 06)

For subjects who undergo an LP for collection of CSF: Subjects who are on anticoagulants may have a variable dose but should have stable anticoagulation control for at least 4 weeks before the LP procedure. Subjects may be required to stop their anticoagulant medication before CSF collection and then restart this medication after the LP procedure, as per local guidelines.

Either aspirin or clopidogrel (or any other antiplatelet drug that is not aspirin) is permitted in all subjects. Aspirin and clopidogrel (or any other antiplatelet drug which is not aspirin) in combination are also permitted but subjects who are on such a combination of antiplatelet drugs may be required to stop 1 or more of these antiplatelet drugs before the LP procedure and restart after the LP as per local guidelines.

Subjects who initiate treatment with drugs not intended for treatment of cognitive impairment during the study should continue in the study if in the opinion of the investigator this will not interfere with study procedures or subject safety and are not prohibited above. However, if such drugs may affect cognitive function, subjects should not undertake cognitive assessments until they have been on a stable dose for at least 4 weeks.

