9.3 Selection of Study Population

At least 850 subjects with EAD including MCI due to AD and the early stages of mild AD will be enrolled across up to approximately 250 centers worldwide (revised per Amendment 06). Randomization will be stratified according to region (7 levels), clinical dementia staging, with no more than approximately 25% of the randomized subjects diagnosed with the early stages of mild dementia due to AD, and concurrent AD medication use. (revised per Amendments 01 and 02) Subjects who do not meet all of the inclusion criteria or who meet any of the exclusion criteria will not be eligible to receive study drug.

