7. Subjects must have been on stable doses of all other (ie, non-AD related) permitted concomitant medications for at least 4 weeks before Randomization, except for medications which are administered as short courses (eg, up to 3 weeks unless discussed and agreed with the medical monitor) of treatment (eg, anti-infectives, oral steroids) or which are to be used on a Pro re nata (PRN) basis. Subjects who require a short course of treatment, such as anti-infectives or oral steroids, may be randomized once the acute illness has completely resolved, even if the concomitant medication continues. (revised per Amendment 01)
8. Must have an identified study partner (defined as a person able to support the subject for the duration of the study and who spends at least 8 hours per week with the subject). The study partner must be literate and able to provide written informed consent. (revised per

Amendment 04) In addition, this person must be willing and able to provide follow-up information on the subject throughout the course of the study. This person must, in the opinion of the investigator, spend sufficient time with the subject on a regular basis such that they can reliably fulfill the requirements of being a study partner. A study partner need not be living in the same residence with the subject. For such a study partner not residing with the subject, the investigator has to be satisfied that the subject can contact the study partner readily during the times when the study partner is not with the subject. Study partners need to provide input to the following assessments: CDR, FAQ, EQ-5D, QOL-AD, Zarit's Burden Interview, NPI-10, and the clinical assessment of suicidality. (revised per Amendment 01) Consideration can occur for the investigator to decide whether the study partner can provide information over the telephone or whether the study partner must attend the study visits in person with the subject.

9. Provide written informed consent. Subjects must, in the investigator's judgment, have the capacity to consent (capacity to consent should be determined in accordance with applicable professional standards and local laws/regulations). (revised per Amendment 04)

For inclusion criteria specific to the Extension Phase, refer to [Appendix 5 in Section 12](#).

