- Subjects with seasonal or perennial allergic rhinitis, asthma, or chronic obstructive pulmonary disease where the condition is considered to be stable and adequately controlled by inhaled steroids.
- Hashimoto's thyroiditis but who are stable on thyroid replacement therapy and not on systemic immunosuppressive therapy.
- Cutaneous manifestations of immunological disease that do not require systemic immunosuppressive therapy or systemic immunomodulatory therapy (ie, topical steroid treatment is permitted)

13. Any other clinically significant abnormalities, such as:

- Physical examination or vital signs at Screening or Baseline which in the opinion of the investigator require further investigation or treatment or which may interfere with study procedures or safety. (revised per Amendment 04)
- Laboratory tests or ECG at Screening that in the opinion of the investigator require further investigation or treatment or may interfere with study procedures or safety. (revised per Amendment 04)
- Other medical conditions (eg, cardiac, respiratory, gastrointestinal, psychiatric, renal disease) which are not adequately and stably controlled, or which in the opinion of the investigator(s) could affect the subject's safety or interfere with the study assessments (revised per Amendment 02)
- Illiteracy, or severe visual or hearing impairment that would prevent the subject from performing psychometric tests accurately (revised per Amendment 01)

14. A prolonged QTcF interval (QTcF greater than 450 ms according to central reading at Screening). (revised per Amendment 04) If the QTcF machine read is greater than 440 ms on the first single 12-lead ECG, 2 additional 12-lead ECGs will be performed 1 minute apart and the mean of the 3 QTcF values will be calculated. (revised per Amendment 06)

15. Malignant neoplasms within 5 years of Screening (except for basal or squamous cell carcinoma in situ of the skin, or localized prostate cancer in male subjects with treatment cycles completed at least 6 months before Screening). Subjects who had malignant neoplasms but who have had at least 5 years of documented uninterrupted remission before Screening need not be excluded. (revised per Amendment 01)

16. Hypopigmentation conditions (eg, albinism and vitiligo). Hypopigmentation associated with scarring need not be exclusionary

17. Known or suspected history of drug or alcohol abuse or dependence within 2 years before Screening

18. Taking prohibited medications

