Appendix 2 List of Permitted and Prohibited Prior/Concomitant Medications

Prohibited medications are shown in [Listing 1](#), [Listing 2](#), and [Listing 3](#). Medications permitted with restrictions are listed in [Listing 4](#), [Listing 5](#), and [Listing 6](#). These may not be all-inclusive listings. Please contact the medical monitor(s) if the investigators have any questions or concerns regarding any medication not listed that your subjects may be taking before enrollment or start during the course of the E2609-G000-301 study.

Antibiotics, analgesics, and anti-inflammatory drugs intended for short courses of treatment are permitted and do not need to follow the restrictions of [Listing 6](#) for a stable dose of 4 weeks before Baseline. If these medications may affect cognitive function but the medications are clinically indicated, then cognitive testing should not take place until at least 72 hours after the last dose of the course of treatment.

Prohibited Prior/Concomitant Medications

Listing 1 Prohibited Medications Within 5 Half Lives or 7 Days, Whichever is Longer, Before Randomization and Until the Last Visit During the Treatment Period

Moderate to Strong Inhibitors of Carboxylesterase 2 (CES2) Enzyme Activity
Generic name
Loperamide
Orlistat
Telmisartan
Fenofibrate
Carvedilol
Manidipine
Diltiazem
Verapamil
Itraconazole (revised per Amendment 04)

NOTE: Simvastatin use is permitted only with once daily evening administration.

Listing 2 Prohibited Medications Within 5 Half Lives or 60 Days, Whichever is Longer, Before Baseline and Until the Last Visit During the Treatment Period

Systemic Immunosuppressants^a and Immunomodulatory Drugs (revised per Amendments 02 and 04)	
Prednisolone	Deltasone, Prednicot, Prednisone Intensol, Rayos, Sterapred, Sterapred DS
Methylprednisolone	Medrol, Meprolone
Dexamethasone	Decadron, Dexasone, Diodes, Hexadrol, Maxidex
Azathioprine	Azasan, Imur
Mycophenolate	CellCept, Myfortic
Fingolimod	Gilenya
Methotrexate	Trexall
Ciclosporine	Gengraf, Neoral

Prohibited Medications Within 6 Months Before Screening and Until the Last Visit During the Treatment Period (revised per Amendment 02)

Immunoglobulin Therapy and Biologic Drugs (revised per Amendment 02)	
Ranibizumab	Lucentis
Bevacizumab	Avastin
Infliximab	Remicade
Etanercept	Enbrel
Adalimumab	Humira
Omalizumab	Xolair
Efalizumab	Raptiva

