Immune globulin IV, IVIG, IGIV	Carimune, Flebogamma, Gamimune N, Gammagard, Gamunex, Gammar-P IV, Iveegam, Octagam, Panglobulin, Vigam, Polygam S/D, Privigen, Sandoglobulin, Venoglobulin-S
Denosumab	Prolia (revised per Amendment 02)
Other monoclonal antibodies not listed here	

^a Topical, ocular, and inhaled formulations with minimal systemic exposure need not be prohibited. (revised per Amendment 04)

Listing 3 Prohibited Live/Live Attenuated Vaccines Within 3 Months Before Randomization and Until the Last Visit During the Treatment Period (this does not apply to non-live/inactivated vaccines)

Bacterial vaccines	Viral vaccines
Bacillus Calmette-Guérin vaccine against tuberculosis	Measles vaccination
Typhoid vaccination (oral)	Mumps vaccination
Cholera vaccination (oral)	Rubella vaccination
	Oral polio vaccination (Sabin)
	Yellow fever vaccination
	Varicella (chickenpox) vaccination
	Rotavirus vaccination
	Japanese encephalitis vaccination
	Live attenuated influenza vaccine (FluMist in the United States and Canada, and Fluenz in Europe)

This list is not exhaustive

Permitted Prior/Concomitant Medications

Listing 4 Medications Which Need To Be on a Stable Dose for 12 Weeks Before the Cognitive Assessments at Visit 2

Cognitive Enhancers	
Donepezil	Aricept
Rivastigmine	Exelon
Galantamine	Reminyl
Memantine	Namenda

Initiation, termination or change in dose is permitted if in line with local standard of care. Any changes are required to be stable for 4 weeks before any cognitive assessments.

Herbal medications or preparations should be discussed with the medical monitor. However, if they have claims of cognitive enhancements then they should follow the same rules as the medications in this listing. (revised per Amendment 06)

**Listing 5 Medications Permitted if Used on PRN or Short Term Basis (2 to 4 Weeks)
Which Are Not to be Used Within 72 Hours Before Cognitive Testing**

Generic name	Trade name
Benzodiazepines (revised per Amendments 04 and 06)	
Estazolam	ProSom
Alprazolam	Alprazolam Intensol, Niravam, Xanax
Triazolam	Halcion
Midazolam	Versed
Lorazepam	Ativan
Flunitrazepam	Rohypnol
Temazepam	Restoril
Clonazepam	Ceberclon, Klonopin
Diazepam	Diastat, Dizac, Valium
Chlordiazepoxide	H-Tran, Librium
Flurazepam	Dalmane
Sedatives	
Zopiclone	(various)
Zolpidem	Ambien; others
Ramelteon	Rozerem
Amitriptyline	(various)
Dothiepin	(various)
Risperidone	Risperdal
Olanzapine	Zyprexa
Promethazine	Phenergan; others

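### Inclusion 7 lets a subject be randomized while still taking a short course of oral steroids, but Section 9.4.7(b) and Listing 2 bar systemic steroids for at least 60 days before randomization

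*Protocol*

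**What the plan says.** All passages are from the current text of the protocol.

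- **Section 9.3.1, Inclusion 7.** The first sentence requires permitted non-AD medications to be stable for 4 weeks before randomization. It excepts short courses and gives oral steroids as an example. The last sentence turns to subjects who need such a course and says that those on drugs "such as anti-infectives or oral steroids, may be randomized once the acute illness has completely resolved, even if the concomitant medication continues".
- **Section 9.4.7, on other medications.** The same 4-week rule appears with the same exception, for "short courses (eg, up to 3 weeks unless discussed and agreed with the medical monitor) of treatment (eg, anti-infectives, oral steroids".
- **Section 9.4.7(b).** The rule reads: "Systemic immunosuppressive or immunomodulatory drugs are not permitted for a period of 5 half-lives or 60 days (whichever is longer) before randomization". The ban then runs on to the final visit on treatment.
- **Appendix 2, Listing 2.** The heading reads "Prohibited Medications Within 5 Half Lives or 60 Days, Whichever is Longer, Before Baseline and Until the Last Visit During the Treatment Period". The table lists prednisolone, methylprednisolone and dexamethasone by name. The footnote gives the only relief: "Topical, ocular, and inhaled formulations with minimal systemic exposure need not be prohibited".
- **Section 9.3.2, Exclusion 18.** "Taking prohibited medications" is an exclusion criterion. Section 9.3 adds that subjects "who meet any of the exclusion criteria will not be eligible to receive study drug".
- **Appendix 2, introduction.** Short courses of antibiotics, analgesics and anti-inflammatory drugs are said to be allowed, and are released from the Listing 6 requirement of 4 weeks on a stable dose. The sentence does not mention Listing 2.

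**The concern.** A site that follows the last sentence of Inclusion 7 exactly, for one of the steroids in Listing 2, randomizes a subject whom the medication rules exclude. A site that starts from Listing 2 turns the same subject away. Each can cite the protocol, and up to approximately 250 centers have to apply it.

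The ban on systemic immunosuppressants is an immune-safety rule. Section 7.1 reports some reduction in CD4 counts at 50 to 100 mg in the multiple-dose study, a range that includes the 50 mg trial dose. At stake are consistent eligibility decisions, avoidable deviations, and steroid exposure in subjects whom this rule was meant to keep out.

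**Working it through.** No figure in the plan needs reproducing. The check sets the passages against each other for one concrete subject, who is taking prednisolone on Day 1 for an acute illness that has resolved.

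1. **Inclusion 7, last sentence.** The illness has resolved and the drug continues. Randomization is allowed. Required clearance: 0 days.
2. **Section 9.4.7(b) and Listing 2.** The clearance is the longer of 5 half-lives and 60 days. Whatever the half-life, it cannot be less than 60 days. Listing 2 counts from baseline and 9.4.7(b) from randomization, but both fall at Visit 2, so the two agree.
3. **Difference.** At least 60 − 0 = 60 days. In addition, any dose after Day 1 falls inside the on-treatment part of the ban.
4. **Does an exemption reach oral steroids?** The 60-day table of Listing 2 names 8 drugs: prednisolone, methylprednisolone, dexamethasone, azathioprine, mycophenolate, fingolimod, methotrexate and ciclosporine. Three of the 8 are corticosteroids. The footnote exempts 3 routes (topical, ocular, inhaled), and oral is not among them. Neither 9.4.7(b) nor Listing 2 has a short-course exemption.
5. **Which rule governs?** The subject is taking a Listing 2 drug and so meets Exclusion 18. Section 9.3 makes anyone who meets an exclusion criterion ineligible. Together these point to exclusion. This is an inference from two general provisions, because no sentence says that Listing 2 overrides Inclusion 7 or the reverse.
6. **Do the other short-course passages resolve it?** The first sentence of Inclusion 7 and its counterpart in 9.4.7 are exceptions to the stability rule, not to the ban, but both use oral steroids as the example. The Appendix 2 introduction waives the Listing 6 stability rule. It also says outright that short anti-inflammatory courses are allowed, and a site could take that to include steroids. These passages add to the conflict.

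**The case against.** The strongest reply is that the short-course wording is a deliberate, specific exception to a general ban. It names oral steroids, it appears in both Inclusion 7 and 9.4.7, and the permissive sentence in Appendix 2 stands above all the listings. This cannot be ruled out, and it is why the precedence of the exclusion must be called an inference. It does not remove the conflict. The place for such an exception is 9.4.7(b) or Listing 2, and neither has one. By the in-text tags, the Inclusion 7 sentence dates from Amendment 01, while 9.4.7(b) and the Listing 2 footnote were revised again by Amendment 04. The exemptions were therefore revisited later without adding short oral courses.

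A second reply is that Inclusion 7 covers only permitted medications. That word limits its first sentence. The last sentence does not repeat it, and reading it in would leave the oral-steroid example empty for the listed drugs.

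A reader might also infer that the rule during treatment is unclear. The documents do not support that. Section 9.4.7(b) runs expressly to the last Treatment Period visit, and the same section lets subjects who start new drugs continue only if "this will not interfere with study procedures or subject safety and are not prohibited above". On those provisions a systemic steroid during treatment is simply banned.

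Nor should the safety argument be pressed further. Section 7.1 links a possible rise in infection risk to CD4 and CD8 falling close to or below the lower limit of normal at 200 and 400 mg, not at the trial dose.

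**Conclusion.** The conflict is real and lies in the operative text. For the same subject, Inclusion 7 requires 0 days of clearance from oral steroids, while 9.4.7(b) and Listing 2 require at least 60. The better reading is that the subject is ineligible. That rests on Exclusion 18 combined with Section 9.3, and on taking Listing 2 at its word that the three named corticosteroids belong to the barred class. The documents do not show which rule the sponsor intended.

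The consequence is limited. Exclusion 9 (low absolute lymphocyte count), Exclusion 10 (active infection within 4 weeks), hematology at every visit, and the interruption rules in Section 9.3.3 for confirmed counts below 800/mm³ or severe infection all reduce the harm. The protocol gives no frequency of steroid courses, so the number of subjects affected cannot be estimated. A reader might infer a threat to the primary result, but no sample size, alpha, power or primary-analysis figure depends on this. It should be corrected as a wording defect with a bearing on eligibility and safety.

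**What to change.** **Default.** Delete oral steroids as an example from both sentences of Inclusion 7 and from the short-course sentence in 9.4.7, so that 9.4.7(b) and Listing 2 govern. In the same amendment, state in the Appendix 2 introduction that its short-course sentence waives only the Listing 6 stable-dose rule and does not lift Listings 1 to 3. This second edit is required. Without it, the Appendix 2 permission for short anti-inflammatory courses would still compete with Listing 2.

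**Alternative, if the sponsor did intend to allow short courses.** Write an explicit exemption into 9.4.7(b) and Listing 2, with a maximum duration and a prerandomization washout in days. State whether it applies during the Treatment Period. Limit the Inclusion 7 permission to randomize while the drug continues to drugs other than systemic steroids.

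**Cost.** Either route is a clarifying amendment to wording, with no new assessment. Under the default, a short systemic steroid course in the 60 days before randomization delays or excludes the subject, and one during treatment is a protocol deviation. This includes subjects with asthma or COPD, whom the Exclusion 12 note admits when stable on inhaled steroids. Under the alternative, some short steroid exposure is accepted in a trial that monitors lymphocytes.
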